5.3 Subject Randomization

On Day 1 (Visit 2), subjects (no more than 60% of either sex) will be randomized to one of four product-use order sequences in a 1:1:1:1 ratio (n = ~8 subjects from each subpopulation in each sequence: A B D C, B C A D, C D B A, D A C B). Subjects will also be randomized by sex.

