14. have used medication for depression or asthma within 12 months of Visit 1 (screening) and Visit 2;
15. have a history of drug or alcohol abuse within 12 months of Visit 1 (screening) and Visit 2;
16. have had allergic or other known adverse reactions to menthol, propylene glycol, or glycerol;
17. if female, be pregnant, nursing, or planning to become pregnant during the study;
18. have participated in a clinical study for an investigational drug, medical device, biologic, or for a tobacco product within 30 days before Visit 1 (screening) and Visit 2;
19. be a current or former employee of the tobacco industry or a first-degree relative (e.g., parent, spouse, sibling, child) of a current or former employee of the tobacco industry or a named party or class representative in litigation with any tobacco company;
20. have been involved in the development of the study design or conduct or be a first-degree relative (e.g., parent, spouse, sibling, child) of someone involved in the development of the study design or conduct;
21. be a current employee or personnel involved with the study at the site; or
22. have participated in two or more ALCS studies within the 12 months period before Visit 1 (screening) and check-in at Visit 2.

Study Duration:

The expected study duration from subject Visit 1 (screening) to the End of Study for each individual subject will be approximately 34 days.

Statistical Analysis:

Descriptive statistics (number of observations, number of missing, mean, SD, median, minimum, maximum, the first quartile, the third quartile, 95% confidence interval, and coefficient of variation) will be provided for each analyte level (defined as the difference between the product sample value and the sham sample value), puff duration, number of puffs per cartridge, and for cartridge weight change by test product and use session (exhaled breath or ad libitum use). A linear mixed model for analysis of variance will be used on the analyte level in the exhaled breath samples, average puff duration, average puff flow rate, average puff volume, average puff number per cartridge, and cartridge weight changes. The model will include sequence, study product, and period as fixed effects and subject nested within-sequence

SYNOPSIS (continued)

as a random effect. Additional details of the statistical analysis will be provided in the statistical analysis plan.

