9.5.2 Exhaled Breath Analytes, Puff Topography and Cartridge Weights

Descriptive statistics (number of observations, number of missing, mean, SD, median, minimum, maximum, the first quartile, the third quartile, 95% confidence interval, and coefficient of variation) will be provided for each analyte level (defined as the difference between the product sample value and the sham sample value), average puff duration, average flow rate, average puff volume, average number of puffs per cartridge, and for cartridge weight change by test product and use session (exhaled breath or ad libitum use). Separate linear mixed model for analysis of variance will be used to estimate effects of test product on the (1) each analyte level in the exhaled breath samples, (2) average puff duration, (3) average puff flow rate, (4) average puff

volume, (5) average puff number per cartridge, and (6) cartridge weight changes. The models will include sequence, study product, and period as fixed effects and subject nested within-sequence as a random effect. A frequency table will be used for the response to the Use the Product Again Questionnaire. Additional details of the statistical analysis will be provided in the statistical analysis plan.

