1.6 RANDOMIZATION

Each subject will be assigned to one of 4 test product sequences using a Williams design. The Williams design employs a Latin square, in which no test-product follows another specific test-product more than once in a given replication of the experiment (e.g., B will never follow A more than once in a 4x4 crossover design matrix). This property yields a balanced cross-over design wherein there is uniformity within both periods and sequences. In a balanced design, each of the test product types occurs the same number of times in each period and the number of subjects who receive test product type i in one period and test product type j in the next period is the same for all $i \neq j$ (Jones and Kenward 2003).

For this study, if the 4 test products are designated A, B, C, and D, the following 4x4 matrix (Table 2) represents one possible assignment of the 4 possible sequences to 4 different subjects. Thus the matrix represents one complete replication of the 4-period-4-sequence crossover experiment.

Table 2. Test Product Type Assignment in a Single Replication of a 4x4 Williams Crossover Design

Sequence	Test product type Assignment By Period			
	1	2	3	4
1	A	B	D	C
2	B	C	A	D
3	C	D	B	A
4	D	A	C	B

The randomizations will be done using a SAS macro program.^[6]

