2. When the amounts of analyte in pad(s) and tube are both below MDL; EBS value will be the sum of the two MDL values. However, since the MDL is volume dependent, the sum will be considered as below MDL (i.e. <0.5).
3. When the amount of one analyte is MDL, but the other is above MDL. EBS will be the sum of the MDL value and the above BLLOQ value.

Descriptive statistics (number of observations, number of missing, mean, SD, median, minimum, maximum, the first quartile, the third quartile, 95% confidence interval, and coefficient of variation) will be tabulated for each of these analytes by test product. Frequency (n and %) of MDL values will be summarized for each product. If the percentage of MDL values for an analyte is more than 50% in any product group, the analyte will not be analyzed with a mixed model.

Statistical Analysis Plan

Each mixed model will be fit to the data by restricted maximum likelihoods. Covariance structures to account for dependencies among repeated measures, within subjects, will be selected for each model using AIC criteria.^[11] Four candidate covariance structures will be considered: compound symmetry, 1st order autoregressive, 1st order autoregressive with a random subject effect, and unstructured. Each model will include period-specific sham values (as a covariate), sequence, study product, and period as fixed effects; subjects nested within-sequence will be modeled as random effects. Standard residual analyses will be used to examine validity of assumptions for the fixed effect distributions. Response variables will be appropriately transformed (e.g., log, reciprocal, or square root) if the residuals indicate distributional assumptions don't hold. The models will be refit to the transformed data and residual analyses again be performed verify that the transformations corrected the problems.

Mean SCA response with (95% confidence limits), for each test product, will be estimated using SAS Least square means methods in each model. Estimates will be back-transformed to the original scale as necessary. Analyte LSmean estimates (with 95% CIs) for each test product will be tabulated for each model. As an example, the SAS Proc Mixed code to fit the Mixed effects ANCOVA model [with an AR(1) covariance structure] is provided below:

```
ods graphics on;
proc mixed data=evap_data method=REML;
  class seq test_product period subject;
  model Analyte = sham § seq period test_product/residual DDFM=KR;
  Random subject (seq); †

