  Repeated /type=AR(1) subject=subject(seq); ‡
  lsmeans test_product/cl alpha=0.05;
  ods output lsmeans=mndat;
  title1 'Fit a 4x4 crossover design mixed effects ANCOVA';
  title2 'with a baseline(sham) covariate adjustment'; run;
```

§ amount (µg) of exhaled analyte from sham is entered in the model as a “baseline” covariate
† explicit inclusion of the subject in a random statement will depend upon the selected covariance structure (Little et al. 2000).
‡ AR1 requires a Random subjects statement, but the UN structure does not.

Statistical Analysis Plan

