7.2 ANALYSIS OF SECONDARY RESPONSE ENDPOINTS

Descriptive Statistics (n, mean, SD, Qtr1, median, Qtr3 and CV) will be provided, by product, for the following measurements:

- Exhaled breath sessions
 - Cartridge weight change by sampling session and overall
- 12 hour ad-libitum use session
 - Cartridge weight change by cartridge and overall (Template provided)
 - Total cartridge weight change (Template provided)
 - Number of cartridges used
 - Puff count by cartridge and overall
 - Total puff count
 - Average puff duration by cartridge and overall
 - Total puff duration by cartridge and overall
 - Average puff duration of the total puffs
 - Total puff duration
- Complete cartridge use over 12-hour ad-libitum use session
 - Puff count per complete cartridge (Template provided)
 - Average puff duration per complete cartridge
 - Total puff duration per complete cartridge
 - Cartridge weight change per complete cartridge

Definition of complete cartridge use: If a subject replaced a cartridge with a new cartridge, the previous cartridge is considered a complete cartridge. If subject only used one cartridge for the day, none would be counted as complete cartridge.

Mixed models will be applied to the following measurements:

- Total puff count over the 12-hour ad-libitum use session

Statistical Analysis Plan

- Total puff duration over the 12-hour ad-lib use session
- Average puff duration of the total puffs over the 12-hour ad-lib use session
- Total cartridge weight change over the 12-hour ad-lib use session
- Cartridge weight change calculated in each exhaled breath sampling session

Each model will include fixed effect terms for product, period and sequence. Subjects within sequence will be modeled as random effects. Models will be fit with SAS Proc Mixed, using the procedures described in Section 7.1.

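### Sex is named as a randomisation factor but is in no planned model; adding it in the SAP is a cheap way to narrow the per-product intervals slightly, and corrects no error

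*Protocol*

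**What the plan says.** Protocol 5.3, and the randomisation paragraph of the Synopsis, allocate about 32 subjects 1:1:1:1 to four product orders, with at most 60% of either sex, and add: "Subjects will also be randomized by sex". SAP 1.6 describes only the sequence assignment and does not mention sex: "Each subject will be assigned to one of 4 test product sequences using a Williams design".

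The models leave sex out everywhere:

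- Protocol Synopsis, Statistical Analysis: "The model will include sequence, study product, and period as fixed effects and subject nested within-sequence" (as a random effect).
- Protocol 9.5.2: "The models will include sequence, study product, and period as fixed effects and subject nested within-sequence as a random effect".
- SAP 7.1, primary analytes: "Each model will include period-specific sham values (as a covariate), sequence, study product, and period as fixed effects", with subject within sequence as random. The SAS code has the same terms.
- SAP 7.2, cartridge weight and puffing outcomes: "Each model will include fixed effect terms for product, period and sequence".

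The reported primary quantity is a mean per product: "Mean SCA response with (95% confidence limits), for each test product, will be estimated using SAS Least square means methods in each model". The code requests it with "lsmeans test_product/cl alpha=0.05". The Synopsis and Protocol 9.5.2 leave further analysis details to the SAP.

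**The concern.** Sex cannot be assigned at random, so the protocol's sentence most plausibly means that sequences are allocated within sex. A factor used to balance the allocation is usually carried into the analysis. Here it disappears without comment.

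In many crossover trials this would hardly matter, because the target is a within-subject contrast and sex cancels. Here the primary objective is the sham-corrected amount for each product, intended for modelling exposure of non-users. The variance of a product mean includes between-subject variance, so any difference between men and women in the amount exhaled stays in the interval. At stake is a small amount of precision in the trial's main output. The sample size of 32 comes with no precision target in either document.

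**Working it through.** **The plan's own figure.** SAP 1.5 says 32 subjects give 8 replications of each sequence: 32 / 4 = 8. This reproduces. There is no power or width calculation to check.

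**Inputs from the documents.** 32 subjects, 4 sequences, 4 periods, a 95% interval per product, and at most 60% of either sex (0.6 × 32 = 19.2, so the most uneven split is 19/13).

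**Assumptions, not in the documents.** ICC of 0.3, 0.5 or 0.7; R², the share of between-subject variance explained by sex, from 0 to 20%; complete data, compound symmetry, no sham covariate, total variance 1.

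**Formula.** With between-subject variance σb² = ICC × (1 − R²) in the model with sex (σb² = ICC without it) and within-subject variance σw² = 1 − ICC:

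- MSb = σw² + 4σb², on 32 − 4 = 28 df without sex and 27 df with sex
- MSw = σw², on 90 df
- Var(product mean) = (MSb + 3MSw) / (4 × 32)
- Satterthwaite df = (MSb + 3MSw)² / (MSb²/df_b + (3MSw)²/90), where df_b is 28 or 27
- half-width = t(0.975, df) × √Var

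**Worked case, ICC 0.5.**

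- Without sex: MSb = 0.5 + 4 × 0.5 = 2.5 and 3MSw = 1.5. Var = 4.0/128 = 0.03125; df = 16/(6.25/28 + 2.25/90) = 64.5; t = 1.9975; half-width 0.3531 SD.
- With sex, R² = 10%: MSb = 0.5 + 4 × 0.45 = 2.3. Var = 3.8/128 = 0.02969; df = 14.44/(5.29/27 + 2.25/90) = 65.4; t = 1.9969; half-width 0.3441 SD.
- Ratio 0.3441/0.3531, about 2.6% narrower.

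**All settings** (half-width in SD; change against no sex term):

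| ICC | No sex term | R² = 0 | R² = 2% | R² = 5% | R² = 10% | R² = 20% |
|---|---|---|---|---|---|---|
| 0.3 | 0.3512 | 0.3513 (+0.04%) | 0.3502 (−0.3%) | 0.3486 (−0.7%) | 0.3459 (−1.5%) | 0.3403 (−3.1%) |
| 0.5 | 0.3531 | 0.3533 (+0.06%) | 0.3515 (−0.5%) | 0.3487 (−1.2%) | 0.3441 (−2.6%) | 0.3346 (−5.25%) |
| 0.7 | 0.3560 | 0.3563 (+0.10%) | 0.3537 (−0.6%) | 0.3498 (−1.7%) | 0.3432 (−3.6%) | 0.3297 (−7.4%) |

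Break-even is at R² of about 0.24% to 0.27%.

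**Weighting of the two sexes.** The table holds for 16/16, and for 19/13 if sex is evaluated at the enrolled proportion. If sex were instead added as a CLASS factor, LSMEANS would weight men and women equally. At 19/13 the between-subject part of the variance would then rise by a factor of 1.037. With no sex effect the interval would be 0.9% to 1.6% wider, and break-even would move to R² of about 4% to 6%. Centring avoids this.

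**One trial rather than the average.** I simulated 200,000 draws per setting (16/16, same model). The realised interval comes out wider with sex than without in 68% to 69% of trials at R² = 0, 41% to 47% at 5%, 22% to 32% at 10% and 5% to 13% at 20%.

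**Other model forms.** For R² of 10% to 20%, GLS standard errors with a period-specific sham covariate independent of sex are 1.5% to 7.25% narrower. With AR(1) (correlation 0.4) plus a random subject effect they are 1.6% to 7.4% narrower. The standard error of a product contrast changes by 0.02% or less. The unstructured covariance option was not checked.

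**The case against.** The strongest objection is that this is a preference. The protocol and SAP models agree in leaving sex out, no objective or endpoint concerns sex, the sample size is described as descriptive and practical, and Protocol 9.5.2 presents the models as estimating product effects, for which sex cancels. The gain depends on a sex effect that nobody has quantified. All of this is correct, and it is why the point is minor. It does not remove the point, because SAP 7.1 reports a mean per product and the expected loss is at most 0.1% if sex does not matter.

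Three further points stand:

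- Conditioning on the enrolled sex mix changes what the interval describes. In simulations (12,000 trials per setting, Monte Carlo error about 0.2 points), coverage of a 50:50 population mean was 95.1% to 96.2% without sex and 94.5% to 94.8% with it.
- If sham values already carry part of any sex effect, the gain shrinks.
- Stratification is inferred from loose wording, and SAP 1.6 does not confirm it.

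A reader might infer that leaving out a stratification factor makes the planned intervals wrong. The documents do not support that. For the enrolled sex mix, simulated coverage without sex was 95.1% to 96.9%, which is valid and slightly conservative, and with complete data neither means nor contrasts are biased. A reader might also infer that the protocol and SAP models conflict over sex. They do not: both omit it. Nor is the change free.

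**Conclusion.** The point holds as a minor, optional improvement. Sex is stated as a randomisation factor and appears in no model. Adding it would be expected to narrow the per-product intervals by 0.3% to 0.6% if sex explains 2% of between-subject variance, rising to 3.1% to 7.4% if it explains 20%. At 10% to 20%, the gain is equivalent to having between 32 × (0.3512/0.3459)² = 33.0 and 32 × (0.3560/0.3297)² = 37.3 subjects instead of 32.

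These sizes rest on an assumed ICC of 0.3 to 0.7, on assumed R² values and on complete data, and they are averages over trials: with a small sex effect a particular interval may well come out wider. Nothing is gained for product contrasts, for the raw descriptive confidence intervals, or for any analyte left unmodelled because more than half its values in some product group are at the detection limit.

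**What to change.** Change the SAP only. The protocol leaves analysis details to it, and the SAP already added the sham covariate on that basis.

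1. In 7.1 (text and code) and 7.2, add sex as a fixed effect: code it 0/1, subtract the proportion among subjects in that model to give `sexc`, and keep it out of CLASS.
2. Request the means with `lsmeans test_product / cl alpha=0.05 at sexc=0`, and state that the interval refers to the enrolled sex mix.
3. In 1.6, state that assignment to sequence is stratified by sex, if that is what is meant.

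If the sponsor prefers to leave sex out, one sentence giving the reason is enough.

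The cost is one model term, one LSMEANS option and one between-subject degree of freedom (28 to 27). Sex is already collected.

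Editorial only, at the next protocol revision: clarify the sentence on randomising by sex, and reconcile the count of about 8 in Protocol 5.3, which is given per undefined subpopulation within each sequence, with the Synopsis. If the subpopulations were the sexes, that would mean 8 × 2 × 4 = 64 subjects against 32. This does not justify a protocol amendment by itself.

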5.4 Other Clinical Considerations

5.4.1 Study Restrictions

The following restrictions must be observed during the study:

- No food or beverages are allowed while at the clinical site except as provided by the investigator at the clinical site or approved by the investigator in consultation with the sponsor ([Section 5.4.2](#)).
- No food or beverages containing alcohol are to be consumed in the 48 hours before each Check-in or while at the site.
- No other tobacco or nicotine containing products (other than the test products) will be used while at the research site

Subjects will be informed as to the clinic areas where product use will be allowed. Furthermore, subjects will be instructed to only use the supplied product and not to share the supplied product with anyone. Sharing or exchanging of products with another subject is not allowed and may result in dismissal from the study at the discretion of the investigator or sponsor.

5.4.2 Meal Schedule

Standard meals and snacks will be served at appropriate times (not to occur during exhaled breath collections) as determined by the clinic while subjects are at the clinical site. All subjects will receive the same meals/snacks. Time of meals and snacks (start and stop) will be recorded.

Water will be provided as needed during the study, and subjects will be encouraged to maintain their usual hydration habits.

6.0 Study Materials

6.1 Study Products

The test EVPs that will be used in the study are listed in [Table 2](#). The test products consist of unbranded, open-label, CVR2.6.8 e-vapor. Each consists of a standard battery (BVR2.3) and cartridge (CVR2.6.8). Sham products will consist of inactivated BVR2.3 batteries and empty CVR2.6.8 cartridges. During the 12-hour ad libitum use session, subjects will use the “BVR2.3 REV05 w/ topography v2 batteries” [VR0017D0002] with the assigned test EVP cartridge.

6.1.1 Study Product Accountability

All study products will be provided by the sponsor. Site staff will coordinate shipping of all products from the sponsor or designee. The site will document the contents of all shipments received, the total amount of product used during the study, and the total number of unused product remaining at the end of clinical conduct.

Individual product in-clinic dispensing logs will be maintained by the site for each subject. The logs must include the subject number, date and time each product was dispensed and returned.

6.1.2 Study Product Storage

ALCS will be responsible for ensuring that the quality of the test products provided is adequate for the duration of the study. All study products will be stored in a locked, limited-access area in the site. The products should be stored at room temperature (defined as 15°C to 25°C [59°F to 77°F]; brief excursions to 30°C are acceptable). A

sufficient supply for each subject may be transferred and kept in a secure area in the clinic (e.g., locked drawer or cupboard) each day as necessary, with appropriate documentation of transfer noted as described in [Section 6.1.1](#).

6.1.3 Blinding

This section is not applicable since this will be an open-label study.

6.1.4 Study Product Dispensing

Packaging and labeling details will be provided by the sponsor in a standalone document at a later date.

During use, all cartridge weights will be recorded before and after use (within 90 minutes, except for in between exhaled breath samples, where the weight will be recorded before the next sample is collected). The type of cartridge, time dispensed, and returned time will be recorded for each subject. In addition, dispensing during the ad libitum portion of the study will follow instructions listed in section 5.2.15.

6.1.5 Study Product Retention and Return/Destruction

Ten cartridges of each test product will be retained at the clinical site until finalization of the clinical study report. All other unused study product will be returned to the sponsor or destroyed at the direction of the sponsor. All returns or destruction of products will be documented. Upon finalization of the clinical study report, the sponsor will notify the site regarding the return or destruction of the retained products.

Unused product can only be destroyed after being inspected and reconciled by the study monitor or other sponsor designee.

7.0 Data Management

Data management activities will be detailed in the data management plan. Each vendor involved with this study will adhere to Good Documentation Practices and their standard operating procedures covering their respective activities relevant to participation in this study. The investigator will ensure that all data related to the conduct of this study at their site are attributable, legible, contemporaneous, original,

accurate, enduring, and readily accessible. Relevant standard operating procedures will be available for review and auditing purposes as required.

